5.5 Describe the procedure for obtaining intervention group assignment

The study coordinator with the statistician will randomize participants stratified by MCI status. Participants with and without MCI will be randomized in a 1:1 ratio to either piano training or the active control condition of music listening instruction. To ensure balance throughout enrollment, randomization will be stratified by MCI status (present vs. absent) and conducted in varying blocks of participants as designed by Co-I Ji. [name] will generate the stratified permuted random blocks using R. [name] will maintain the random seed and the computer codes and will send the randomization list to the clinical trial coordinator. The treatment allocation will be denoted as A or B and recorded on the randomization form by the clinical trial coordinator. The study coordinator will control access to the randomization list and know whether A (B) stands for intervention (control). Study investigators [name], [name], and [name] will remain blind to participant condition. The testers will remain blind to participant condition. The trainers (including Co-I [name]) and clinical trial coordinator will be aware of participants' randomized condition.

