9.6 Final Data Analyses

Dealing with Score Distribution. We will inspect the distribution of scores to confirm that parametric statistical testing is appropriate. In the event that distributional properties do not support parametric tests, we will compare the results from conventional parametric analyses with (a) results from similar nonparametric testing (e.g., Wilcoxon signed ranks test), (b) results from parametric analyses conducted after the non-normally distributed variables are transformed to improve normality to compare the results with the conventional parametric analyses, and (c) Any illegal values or outliers of $\geq \pm 3z$ will be checked for accuracy with the raw data.

Composite Outcomes. Data reduction in the form of principal component factor analysis (PCA) will be used to derive composite outcomes of CAP, cognition, and everyday function for analyses to reduce the number of comparisons. Baseline data across CAP, cognitive, and everyday function outcomes will be factor analyzed using pairwise deletions. Based on the number of factors derived and factor loadings of the individual measures (.4 or greater), outcome composite scores will be calculated after transforming the baseline data to z scores while taking into account the directional scaling of the items. Post-test scores will be standardized based upon the baseline mean and SD. The baseline factors and loadings will be applied to calculate post-test composite scores.

Preliminary/Descriptive Analyses. Prior to the analyses described below, we will conduct one-way ANOVA or Chi-square analyses as appropriate comparing the randomized groups at baseline on age, race, education, sex, MoCA, GDS, hearing and vision, to ensure that the study randomization procedures were successful. We will also confirm the equivalence of the two randomized conditions by comparing the NICT questionnaire responses. The total across the six items relevant to cognition will be calculated and examined in analyses. If even a marginally significant ($p < .1$) difference is observed for any of these study variables, the pertinent variables will be included as covariates in subsequent analyses.

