Specific Aim 1: To examine the efficacy of piano training to improve CAP, cognition, and everyday function among older adults. We will compare changes in performance for piano training relative to control across the two measurement points (baseline, immediate post-test). We will use the PCA-derived composites of CAP and cognition, and everyday functioning as outcomes. We will use repeated measures analyses of variance within the mixed effects models, examining group as the between-subjects factor and time as the within-subjects factor. The group x time interaction will indicate whether the participants randomized to piano training change at differential rates over time relative to those randomized to the control group. This output will be obtained for each of the composite outcomes (CAP, cognition, and functional abilities). For aim 1 analyses and the composite outcomes of CAP, cognition, and everyday function, we will apply Holm-Bonferroni adjustments¹²⁵ to reduce Type I error. Specifically, the Holm-Bonferroni procedure uses a step-down process whereby p-values are sorted from lowest to highest, then the lowest p-value is used in its raw version, the second lowest p-value is multiplied by two, the third lowest p-value is multiplied by three and so on until the adjusted

p-value reaches or exceeds the pre-specified threshold for statistical significance, in our case a two-tailed p value of .05.

Intent-To-Treat Approach. We expect that some participants will not complete their intended followup according to the protocol for a variety of reasons, generating missing values. Intent-to-treat (ITT) analysis has become a widely accepted method for dealing with this issue. To maximize available information, we will employ statistical techniques that allow for the inclusion of missing data. Specifically, we will use linear mixed effects models to analyze data. This advanced analytical method allows for the inclusion of participants with missing data, so long as data are missing at random and offers flexibility with regard to the specification of the variance/covariance structure, which often leads to improved fit of the analytical model to the actual data. If there is non-ignorable missing data, we will apply pattern-mixture mixed effects models to assess the sensitivity of our findings with regard to missing data¹²⁶.

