Specific Aim 2: To examine the moderating effects of MCI on intervention efficacy. We will also test for moderation effects to determine at what stage along the cognitive status continuum—without MCI vs. MCI—intervention is most effective. To do so, we will examine three-way interactions (MCI x training group x time) for the CAP, cognitive, and everyday function composites. When an interaction is significant, we will stratify analyses by MCI status and examine effect sizes. Effect sizes from pre- to post- training relative to controls will be compared for participants with/without MCI. An alpha of .05 will be used for these analyses.

Participants who score 26 or higher on the MoCA will be defined as no MCI (i.e., cognitively normal). Those participants who score a 20-25 on the MoCA will be defined as MCI if they score a 0.5 on the CDR and have performance at or 1 SD below their age, sex, and education norms on any of the following measures: Trails, Verbal Fluency, Digit Coding, Craft Story Recall, Multilingual Naming Test, or Benson Complex Figure. Those with MoCA scores 20-25 who score 0 on the CDR, but have performance at or 1SD below expected for age, sex, and education will be adjudicated prior to analyses. If an individual scores 20-25 on the MoCA, and 0.5 on the CDR, but has performance above expected on all of the aforementioned measures, their case will be adjudicated prior to analyses. The study physicians will adjudicate such cases prior to coding of MCI status for final analyses.

To quantify the effects of piano training further, in addition to examining composite outcomes as detailed above, we will calculate and report effect sizes for pre-to-post change of piano training relative to controls for each individual measure of CAP, cognition, and everyday function for the sample overall as well as stratified by MCI status and among those who were adherent only (80% or more of sessions completed).

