The randomized groups did not differ in sex, $\chi^2(1)=.787, p=.375$, ethnicity $\chi^2(1)=.167, p=.683$, or race, $\chi^2(1)=.045, p=.832$. The Music Reading Assessment scores did not differ between the two groups, $t(266)=-.958, p=.338$. The randomized groups did not significantly differ in age, $F(1,266)=.293, p=.589$, education, $F(1,266)=.369, p=.544$, MoCA, $F(1,266)=.427, p=.514$, or GDS, $F(1,266)=.943, p=.332$. However, there were marginally significant group differences for PTA in the left ear, $F(1,266)=3.31, p=.070$ and statistically significant group differences for both PTA in the right ear, $F(1,266)=6.69, p=.010$, and visual acuity, $F(1,266)=8.99, p=.003$. The music listening group tended to have worse hearing, while the piano training group tended to have worse visual acuity. See Table 1. The groups also differed significantly in their expectations regarding potential benefits of their randomized group, $F(1,214)=15.07, p<.001$. The piano training group had an average rating of 5.55 while the music listening group had an average rating of 4.99, indicating the piano training condition had higher expectations about the potential effects of their randomized condition. The piano training group also rated their condition as more challenging with 92% agreeing that the intervention was challenging as compared to 86.3% of the music listening group indicating their condition was challenging ($p<.001$).

Principal component analysis with varimax rotation was conducted to reduce the number of variables for analyses. Please see Supplemental Table A for details. The first factor reflected cognitive performance speed and included the Trail Making Test, Digit Coding, and the TEA visual elevator and phone search subtests. The second factor included all three verbal fluency subtests. The third factor reflected CAP and included DDT, DSI, TCS, and WIN. The fourth factor included two indices from the TEA phone search while counting and visual elevator accuracy. The fifth composite included ATTR across- and within- channel performance. Baseline composites of cognitive performance, verbal fluency, ATTR, CAP, and everyday function were created by averaging z scores after the reverse-scaling of items with negative factor loadings. Post-test scores were standardized

by baseline means and *SDs*. Timed IADL performance did not significantly load on any factor and was thus examined separately.

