In the primary analyses, we examined whether performance changed differentially by random assignment across composite outcomes from baseline to post-test as indicated by a significant group-by-time interaction. Covariates included hearing PTA, visual acuity, and expectations. The group-by-time interactions were not statistically significant for any of the outcomes ($ps > .194$). See Table 2. The results did not change when we included only those who were adherent ($ps > .180$). See Supplementary Table B. Piano training did not significantly enhance CAP, cognition, or everyday function as compared to music listening. We further examined if intervention effects varied by MCI status (Supplementary Table B). There were no significant group-by-time-by-MCI status interactions indicating those with and without MCI did not show differential benefit ($ps > .245$). Thus, MCI did not significantly moderate the effects of piano training.

Effect sizes for piano training as compared to music listening are shown in Table 3. Improvements were not evident in the primary analyses, adherent analyses, or the subsample without MCI on measures of CAP, cognition, or everyday function. Participants with MCI randomized to piano training showed potential small effect sizes for improvement relative to music listening on Trails A, Digit Symbol Coding, and one subtest of the TEA ($ds \geq 0.25$). Raincloud plots of individual assessment and composite variables are included in the supplemental materials.

Results indicated significant effects of time for ATTR in all models and significant effects of time for CAP in the primary and adherent analyses indicating improved performance from pre- to post- training. Significant effects of time were found for cognition and TEA in the primary and adherent analyses, indicating a tendency for decline across time. With respect to covariate effects, CAP, ATTR, and cognitive performance were significantly impacted by hearing. Similarly, Timed IADL and cognitive performance varied significantly by visual acuity. Those with poorer hearing or vision tended to perform worse on these outcomes. Interestingly,

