expectations about the assigned condition were significantly related to composite outcomes of CAP and cognition. However, having greater expectations that the randomized condition would positively affect abilities was associated with poorer performance. See Table 2. Additional sensitivity analyses examined if there were differential effects by sex. No significant group-time-sex interactions were evident ($p > .119$), and the pattern of results was the same when analyses were stratified by sex.

Table 14.1. *Participant characteristics by randomized arm and cognitive status.*

Cognitive status	Piano Training		Music Listening	
	Non-MCI	MCI	Non-MCI	MCI
	M (SD)	M (SD)	M (SD)	M (SD)
	n (%)	n (%)	n (%)	n (%)
Age in years	69.1 (5.5)	71.4 (7.1)	69.6 (5.2)	72.1 (5.7)
Education in years	16.0 (2.3)	16.5 (2.2)	16.0 (2.1)	15.4 (2.3)
Sex (% female)	63 (65%)	18 (48%)	58 (59%)	17 (44%)
Music Reading Assessment score (/40)	2.52 (4.31)	2.43 (3.83)	3.42 (5.41)	2.08 (4.29)
Montreal Cognitive Assessment score (/30)	26.6 (2.1)	23.3 (1.4)	26.6 (1.9)	22.8 (1.6)
Geriatric Depression Scale short-form score (/15)	0.9 (1.2)	1.1 (1.1)	0.9 (1.1)	0.6 (0.9)
Pure tone average left ear (dB)+	19.8 (9.4)	20.4 (9.4)	20.9 (10.8)	27.7 (15.9)
Pure tone average right ear (dB)+*	18.6 (10.3)	20.4 (9.9)	22.4 (14.0)	25.8 (11.6)
Visual acuity (logMAR)+*	.04 (.12)	.09 (.15)	.01 (.13)	.01 (.10)
Expectations (rating/7)*	5.4 (1.2)	5.8 (0.8)	4.9 (0.8)	5.3 (0.8)

Note. MCI=mild cognitive impairment. +Lower scores reflect better performance. *Significant differences by randomized group were evident in pure tone average right ear, visual acuity, and expectations ($ps<.01$).

Table 14.2. *The effects of randomization to piano training as compared to music listening from baseline to post-training across composite outcomes of central auditory processing, cognition, and everyday function.*

	Estimate	SE	p	Estimate	SE	p
	ATTR+			Central auditory processing		
Intercept	53.90	1.17	<.001	46.25	0.73	<.001
Group	-2.24	2.37	.346	-1.72	1.49	.249
Time	-2.77	0.68	<.001	2.29	0.36	<.001
Group x time	1.51	1.35	.265	.465	0.71	.515
Hearing	0.12	0.06	.030	-0.63	0.04	<.001
Visual acuity	6.24	4.71	.187	-7.270	3.97	0.07
Expectations	0.79	0.59	.185	-1.20	0.49	.016
	Verbal fluency			Cognition		
Intercept	49.32	0.98	<.001	51.81	0.90	<.001
Group	-1.81	2.00	.367	-2.62	1.84	.157
Time	0.41	0.48	.393	-1.40	0.42	.001
Group x time	-0.29	0.96	.763	0.39	0.84	.638

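### MCI status, the only randomisation stratum, is missing from the Aim 1 models; adding it with MCI x time is a near-free improvement, and the reported expectations association should be re-checked with it in place

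*Combined protocol and SAP*

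**What the plan says.** Section 5.5 states that "randomization will be stratified by MCI status (present vs. absent"; section 9.1 repeats it, and no other stratification factor is named. Allocation is 1:1 within stratum: "Participants with and without MCI will be randomized in a 1:1 ratio to either piano training or the active control condition".

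Section 9.6, Specific Aim 1, sets up a repeated measures mixed model "examining group as the between-subjects factor and time as the within-subjects factor", with the group x time interaction as the test of efficacy. MCI status is not a term. Covariates come in through the Preliminary/Descriptive Analyses rule: "If even a marginally significant ($p < .1$) difference is observed for any of these study variables, the pertinent variables will be included as covariates". That list contains MoCA but not MCI status. Section 6.3.5 says that eligibility measures, MoCA among them, may be considered as covariates, without committing to it.

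MCI is modelled only under Specific Aim 2: "we will examine three-way interactions (MCI x training group x time) for the CAP, cognitive, and everyday function composites".

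Section 14 gives p = .514 for the MoCA comparison between arms, so the rule did not bring it in. For the primary analyses it states: "Covariates included hearing PTA, visual acuity, and expectations". Table 14.2 agrees, with rows for group, time, group x time, hearing, visual acuity and expectations. From these models section 14 reports that "having greater expectations that the randomized condition would positively affect abilities was associated with poorer performance", for the CAP and cognition composites.

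**The concern.** A model that follows the design carries the factor that randomisation was stratified on. Here that factor would enter Aim 1 only through a test of imbalance between arms, and stratification exists to prevent that imbalance. The rule and the design pull against each other.

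Two things could be at stake. One is the primary test: an omitted stratum that predicts change leaves avoidable noise in the group x time estimate, and it weakens protection if dropout is related to the stratum. The other is how covariate coefficients are read. A coefficient on score level, such as that for expectations, can pick up the effect of an omitted baseline characteristic that relates to both the covariate and the score.

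**Working it through.** **1. The plan's own power figure.** Section 9.3 gives N = 198, f = 0.10, alpha .05 and 95% power for group x time. For a two-occasion within-between interaction, lambda = N f² m / (1 - rho), with m = 2 and df 1 and 196. The correlation rho is not stated.
- rho = .70: lambda = 198 x 0.01 x 2 / 0.30 = 13.2, power 95.1%.
- rho = .50: lambda = 7.92, power 80.0%.

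The figure is reproduced at rho of about .70, which I use below where a correlation is needed.

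**2. MCI share.** The F tests in section 14 have 1 and 266 df, so N = 268. Cell sizes of 96 and 37 (piano non-MCI, MCI) and 97 and 38 (listening) match the counts and percentages of women in Table 14.1, taken as truncated, and return the printed sex chi-square of .787. The share is 75/268 = 28%. In Table 14.3 it is 52/198 = 26%.

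**3. What an MCI main effect does to the primary test.** Change is post minus pre = time + (group x time)·G + (MCI x time)·M + error. The MCI main effect cancels. In a simulation (2,000 runs per scenario, N = 268, 28% MCI, rho .70, MCI 1 SD lower) with complete data, the group x time estimate was identical with and without it.

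**4. Precision.** Share of change variance removed by MCI x time = p(1-p)d² / [1 + p(1-p)d²], with p = .28, p(1-p) = .2016, and d the assumed difference between strata in SDs of change.

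| d | share removed |
|---|---|
| 0.2 | .0081/1.0081 = 0.8% |
| 0.3 | .0181/1.0181 = 1.8% |
| 0.5 | .0504/1.0504 = 4.8% |

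With shifts of 0.2, 0.3 and 0.5 baseline SDs at rho = .70, adding MCI x time moves power from 95.1% to 95.3%, 95.6% and 96.5%. At 0.3, type I error of the unadjusted test is 4.7%, slightly conservative.

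**5. Missing post-tests.** With 24% missing (section 14 reports 76% completing) and no extra dropout by MCI and arm, simulated type I error without MCI was 4.9 to 5.3%. With an assumed 20 points more dropout among MCI piano participants and a 0.3 SD MCI x time effect, the estimate was biased by 0.031 SD and type I error was 6.7%. An MCI main effect reduced the bias to 0.016 SD; MCI x time reduced it to 0.001 SD.

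**6. The reported null.** The smallest group x time p in Table 14.2 is .265 (ATTR): t = 1.51/1.35 = 1.12. Removing 4.8% of variance gives 1.12/√0.952 = 1.15. Reaching 1.97 with the same estimate would need MCI x time to explain 1 - (1.12/1.97)², about 68%, of change variance.

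**7. The expectations coefficient.** Table 14.1 gives piano 5.4 (1.2) non-MCI and 5.8 (0.8) MCI; listening 4.9 (0.8) and 5.3 (0.8). MCI is 0.4 higher in each arm.
- Within-arm variance, piano: .72 x 1.44 + .28 x 0.64 + .2016 x 0.16 = 1.248. Listening: 0.64 + .032 = 0.672. Mean 0.960.
- Slope of MCI on expectations: .2016 x 0.4 / 0.960 = 0.084 per point (0.080 with a 26% share).
- Bias = -(MCI deficit) x slope.

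| Assumed MCI deficit | bias | share of cognition (-1.96) | share of CAP (-1.20) |
|---|---|---|---|
| 5 points | -0.42 | 21% | 35% |
| 10 points | -0.84 | 43% | 70% |

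With standard errors held at 0.64 and 0.49, significance is lost at a deficit of (1.96 - 1.96 x 0.64)/0.084 = 8.4 points for cognition and (1.20 - 1.96 x 0.49)/0.084 = 2.9 points for CAP. Removing the whole association needs 1.96/0.084 = 23 points and 1.20/0.084 = 14 points.

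**The case against.** The best defence is that the primary test is barely touched. Steps 3 to 6 bear this out. A reader might infer that omitting the stratum invalidates the efficacy test or puts the null result in doubt; the documents support neither.

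A reader might also infer that the missing-at-random assumption then holds only given arm and time. That misdescribes a likelihood-based mixed model, which also conditions on each person's observed baseline score and on the covariates fitted. Baseline Trails, Digit Coding and fluency already carry some MCI information, and sections 9.6 and 9.7 plan pattern-mixture sensitivity analyses.

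Setting Table 14.3 against the reconstructed cells, 52/75 = 69% and 146/193 = 76%, may suggest poorer retention in MCI. These are analysed fractions, not retention: section 14 says 19 people were excluded from analysis for events before post-test, the denominators are back-calculated, and the difference has p = .29.

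On expectations, it is tempting to say that the finding is confounded because MCI participants score lower by definition. No composite means by MCI status are given. The MCI definition in section 9.6 contains no CAP test, and one low score on story recall, naming or figure copy, none of them in the composites, can satisfy its test criterion. Hearing is already in the model, with a CAP coefficient of -0.63, and is worse in MCI. Averaging the four MCI minus non-MCI differences in Table 14.1, (0.6 + 1.8 + 6.8 + 3.4)/4 = 3.15 dB, times 0.63, suggests that about 2 points of any CAP gap are already absorbed. The finding is also a side remark on score level, not a hypothesis of the trial.

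What stands: Aim 2 models MCI, but that does not put it into the Aim 1 efficacy model. The direction of the possible bias also comes from the trial's own text: Trails and Digit Coding are in both the MCI definition and the cognitive composite, and the Background (section 3) reports CAP deficits in MCI.

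**Conclusion.** The omission is plain from the text and the tables. For the primary group x time test it is a small loss of efficiency, not a fault of validity: 0.8 to 4.8% of variance under assumed shifts of 0.2 to 0.5 SD of change, with bias only under a dropout pattern that no passage reports.

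The expectations association is open to confounding by MCI; the documents do not establish that it is confounded, or by how much. A bias of -0.4 to -0.8 per expectation point rests on four assumptions: an MCI deficit of 5 to 10 points not adjusted for hearing, composites scaled to an SD of about 10, cell shares reconstructed for all 268 people although only 216 contribute to the expectations comparison (df 1 and 214), and reported cognitive status close to the stratum used at randomisation. The CAP association is the more fragile of the two; full removal of the cognition association would need an implausibly large deficit.

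This is a free improvement of minor to moderate severity.

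**What to change.** State in section 9.6 that every Aim 1 model includes, as fixed terms, the MCI stratum used at randomisation and its interaction with time, whatever the baseline comparisons show. The interaction is needed because a main effect alone does not act on the change contrast in complete data. Use the stratum as randomised even where later adjudication changed a participant's status, and report how many changed; adjudicated status stays in Aim 2.

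Refit the six models in Table 14.2 with these terms. Report composite means by MCI status. Then re-state the expectations sentence from the adjusted coefficients, or add a caveat that the published estimate does not account for MCI.

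The cost is one line in the plan, two degrees of freedom per model and a refit. No new data are needed.

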2 STUDY OBJECTIVES

2.1 Primary Objective

The primary objective is:

- To examine the efficacy of piano training to improve CAP, cognition, and everyday function among older adults across baseline to immediate post-test. We will assess the effects of piano training (intervention) as compared to music listening instruction (active control) on CAP, cognition, and everyday function. The primary outcome of interest is cognition.

Hypotheses: The piano training group will outperform the music listening instruction group on measures of CAP, cognition, and everyday function immediately post-intervention.

Rationale: The efficacy of a novel intervention will be established relative to an active control group. There is compelling evidence that CAP deficits contribute to cognitive difficulties²⁻⁵ and are a risk factor for dementia^{3,6,7}. We propose that enhancing CAP may be particularly important to improve cognitive function. Formal music training is longitudinally associated with enhanced CAP and successful cognitive aging. Piano training is a feasible, potentially efficacious intervention to improve older adults' CAP and cognition.

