9.2.1 Primary outcomes

- To examine the efficacy of piano training to improve CAP, cognition, and everyday function among older adults. We will assess the effects of piano training as compared to music listening instruction on CAP, cognition, and everyday function.

CAP includes Time Compressed Speech, Words-in-Noise, Dichotic Digits Test, Dichotic Sentence Identification and Adaptive Tests of Temporal Resolution. All are parametric tests of perception.

Cognition includes Verbal Fluency (phonemic, category, and switching), Digit Coding, and Trail Making test. All are parametric tests of cognitive function.

Everyday function includes the Timed IADL test and Test of Everyday Attention both parametric measures. Both measures will be examined individually.

Principal Component Analyses (PCA) will be performed with CAP, cognitive and functional measures to form composites of outcomes for use in analyses to reduce the number of comparisons.

Hypotheses: The piano training group will outperform the music listening instruction group on measures of CAP, cognition, and everyday function immediately post-intervention.

Secondary Objectives

The secondary objectives are:

- To examine the moderating effects of MCI on piano training efficacy. Moderating effects of MCI status will determine if piano training is effective for older adults with and/or without MCI. We do not have a directional hypothesis for this objective.
- To explore mediators of intervention effects.

Hypothesis: Grounded in theory⁸ and prior research⁹⁻¹¹, we hypothesize that piano training will improve CAP and cognitive performance, leading to functional improvements. We expect that enhanced CAP will mediate cognitive gains. We further hypothesize that cognitive gains will mediate functional improvements.

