9.3 Sample Size

We expect up to 20% attrition after the initial in-person visit across the time period in which cognitive intervention study protocols will be administered. Our goal is to complete in-person screening visits for up to 450 participants in order to have up to 360 participants complete the study. We can tolerate higher rates of attrition. We require a minimum of 198 eligible participants with *at least* 99 individuals randomized to each condition (piano training, controls) to have adequate statistical power. With stratified randomization, this will result in *at least* 48 persons per MCI/no MCI subgroup.

Statistical power analysis using G*Power¹²³ in consideration of our pilot data effect sizes as well as attrition was conducted to estimate power. We will control type I error at .05 to achieve at least 80% statistical power.

To power **Specific Aim 1: To examine the efficacy of piano training to improve CAP, cognition, and everyday function among older adults**, a final n of 198 participants ($n=99$ per randomized condition) will achieve 95% power to detect a significant group x time interaction across baseline to immediate post-test, with an alpha of .05. This assumes a small effect size (f) of 0.10¹²⁴ (Cohen's f effect sizes are 0.10- small, 0.25- medium: f is roughly equivalent to $\frac{1}{2}$ of d when comparing two groups)¹²⁴.

To power **Specific Aim 2: To examine the moderating effects of MCI on intervention efficacy**, a final n of 168 will have .95 power at alpha .05 to detect medium effects ($f=.10$) for significant group x time x moderator three way interactions.

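### Cognition is named the primary outcome and power is stated at alpha .05, but Aim 1 tests it in a three-composite adjusted family without priority, so neither a .05 test nor 95% power is assured

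*Combined protocol and SAP*

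**What the plan says.** Section 2.1 states: "The primary outcome of interest is cognition". Section 1.3 and the mild cognitive impairment paragraph of section 3 say the same.

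Section 9.2.1, headed as primary outcomes in the plural, ranks none of the three domains: "We will assess the effects of piano training as compared to music listening instruction on CAP, cognition, and everyday function".

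Section 9.3 treats Aim 1 as a single interaction test: "a final n of 198 participants ($n=99$ per randomized condition) will achieve 95% power to detect a significant group x time interaction". The alpha used there is .05 and the assumed effect is f = 0.10. The section also sets a general floor: "We will control type I error at .05 to achieve at least 80% statistical power". It mentions neither multiplicity nor the pre-post correlation.

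Section 9.6, Specific Aim 1, puts the three composites in one family: "For aim 1 analyses and the composite outcomes of CAP, cognition, and everyday function, we will apply Holm-Bonferroni adjustments". It names Holm-Bonferroni, but the steps it spells out leave the smallest p-value unadjusted, double the second and triple the third, against a two-tailed .05. No step gives cognition a test of its own. Under Composite Outcomes, the same section lets the principal component analysis determine how many factors, and so how many composites, there are.

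**The concern.** A trial with one primary outcome normally tests it at the full alpha, and its power statement describes that test. Here the named primary outcome shares alpha with two outcomes that sections 1.3, 2.1 and 3 do not single out, while the power statement uses the unshared alpha. No section reconciles the two.

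Two things are at stake. Whether cognition succeeds can turn on the p-values for central auditory processing (CAP) and everyday function. And a reader of section 9.3 may credit the cognition test with more power than it has.

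**Working it through.** **Inputs.** From section 9.3: N = 198 (99 per arm), f = 0.10, alpha .05, stated power 95%. From section 9.6: two time points, three composites, two-sided .05. Not in the documents: the pre-post correlation r and the correlations between composites. Both are assumptions here.

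**Step 1: reproduce the stated 95%.** For the G*Power within-between interaction with two measurements, λ = f² × N × 2 / (1 − r), with 1 and N − 2 = 196 degrees of freedom.

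- r = .70: λ = 0.01 × 198 × 2 / 0.30 = 13.2; power at .05 is 95.1%.
- r = .60: λ = 3.96 / 0.40 = 9.9; power is 87.9%.
- r = .50: λ = 3.96 / 0.50 = 7.92; power is 80.0%.

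The stated figure is recovered at r of about .70.

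**Step 2: the same test at the stricter Holm steps** (.05/2 = .025 and .05/3 = .0167).

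| r | .05 | .025 | .0167 |
|---|---|---|---|
| .70 | 95.1% | 91.4% | 88.7% |
| .60 | 87.9% | 81.2% | 76.7% |
| .50 | 80.0% | 71.0% | 65.5% |

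Reaching 95% at .0167 with r = .70 takes N = 248.

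**Step 3: the full procedure.** Cognition is not always tested at .0167, so the whole step-down was simulated: 400,000 trials per scenario, between-composite correlations 0, .3 and .6. Power to declare cognition significant at N = 198:

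| Rule | Effect on | r = .70 | r = .50 |
|---|---|---|---|
| Unadjusted .05 | – | 95.1% | 80.0% |
| Standard Holm (×3, ×2, ×1) | cognition only | about 89% | about 66% |
| Standard Holm | all three, f = .10 | 93.2–94.6% | 73–75% |
| As worded in 9.6 (×1, ×2, ×3) | cognition only | 94.8–94.9% | 79.5–79.8% |
| As worded in 9.6 | all three, f = .10 | 89.4–90.2% | 69–70.5% |

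With no true effects, the rule as worded gives a family-wise error of 11.4–13.9%, against 4.0–4.6% for standard Holm. For independent composites the formula is 1 − .95³ = 14.3%.

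**Step 4: a cognition p of .03.**

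| Rank of cognition's p | Standard Holm | As worded |
|---|---|---|
| Smallest | .03 × 3 = .09, fails | .03, passes |
| Second | .03 × 2 = .06, fails | .03 × 2 = .06, fails |
| Largest | .03 × 1 = .03, passes if the two earlier steps pass | .03 × 3 = .09, fails |

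Under either rule the result for cognition depends on the other two composites.

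**The case against.** The strongest reply is that the loss is often small. Under the rule as worded with an effect on cognition alone, or standard Holm with effects on all three (which is the protocol's own hypothesis), power at r = .70 stays within two points of 95%. In every r = .70 scenario it stays above the 80% floor. This stands. A reader might infer that the 95% figure simply does not apply, or that cognition is always tested at .0167. The documents support neither: .0167 is the first step of the cited Holm procedure, whereas the literal wording tests the smallest p at .05.

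Second, a reader might put the whole drop from 95.1% to 65.5% down to multiplicity. It is not all that. Moving r from .70 to .50 costs 95.1 − 80.0 = 15.1 points before any adjustment; the stricter alpha costs a further 80.0 − 65.5 = 14.5. The unstated correlation is a separate weakness of section 9.3.

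Third, 198 is a minimum and the goal is up to 360 completers. At 360, even .0167 gives about 99% (r = .70) or 91.7% (r = .50). That is fair to the plan's ambition, but section 9.3 itself calls 198 adequate, and Table 14.3 reports an overall sample of 198.

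Fourth, three outcomes in one family is a legitimate design and agrees with section 9.2.1. That also stands: the fault is that the plan asserts both designs.

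Finally, no reported conclusion changes. Section 14 gives all group-by-time p-values above .194, and Table 14.2 gives .638 for cognition.

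**Conclusion.** The inconsistency is real and moderate in size. Naming cognition primary, powering at an unadjusted .05 and testing it without priority in a three-composite family cannot all describe one plan. The loss of power for cognition is between nil and about 6 points at r = .70, and between nil and about 14 points at r = .50, depending on which multipliers are used and how many composites have effects. These figures rest on f = .10 from section 9.3, on assumed pre-post correlations and on a family of exactly three. They do not show that the trial was underpowered by its own 80% standard: at r = .70 it was not, and r is unknown.

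Correcting the Holm wording alone would not settle the matter, since standard Holm also gives cognition no assured .05 test.

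**What to change.** Give cognition one role and make the sections agree.

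- **(a) Cognition first.** Test one pre-defined cognition composite at two-sided .05. Only if it is significant, apply Holm, correctly stated (smaller p × 2, larger p × 1), to CAP and everyday function. The power in section 9.3 then describes the primary test, once the assumed correlation is given. The cost is that CAP and everyday function become confirmatory only if cognition succeeds.
- **(b) Three co-primaries.** Remove the single-primary statements from sections 1.3, 2.1 and 3, correct the multipliers to 3, 2, 1 from smallest to largest p, and restate section 9.3 at .0167 with the assumed correlation: about 89% at r = .70. The cost is a lower stated power, or N = 248 to keep 95%.

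Under either option, fix before analysis which composite counts as cognition. The component analysis may split it: the results section reports verbal fluency apart from the cognition composite, and Table 14.2 has six outcomes. A cognition-first gate cannot operate until this is settled.

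Both options are wording changes. As results are already reported, the change here is an annotation of the plan and a clear statement of which rule was applied; re-ordering the tests now would be post hoc.
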